Paired Promotion of Colorectal Cancer and Social Determinants of Health Screening

NCT04585919

06/09/2021

Statistical Design and Power

Study Design: We have chosen a cross-sectional cluster stepped wedge study design. This pragmatic design involves a sequential, randomized roll-out of the intervention across the four participating clinical sites or “clusters” over 8 week intervals or “steps.” The figure below details our approach: 8 months of historical controls at all of the sites (blue pre-COVID and light blue is COVID stay at home) sequential roll out of the base intervention every 8 weeks (yellow), followed by a period of planned adaptation (green).

	Pre-COVID Baseline 10/19-2/20		COVID Stay-at-Home Baseline 3/20-6/20		Stepped-Wedge/Intervention Phase							
	CHC	Mo. 1-2	Mo. 3-4	Mo. 5-6	Mo. 7-8	Mo. 9-10	Mo. 11-12	Mo. 13-14	Mo. 15-16	Mo. 17-18	Mo. 19-20	Mo. 21-22
A												
B												
C												
D												

Outcomes: The primary outcomes in our analysis will be: (1) return of FIT kit within 3 months; (2) completion of social needs screening; (3) referral of patients with social needs to appropriate resources.

Covariates: Age, race/ethnicity, primary language, household income (% of Federal Poverty Level, FPL), insurance, comorbid conditions, number of CHC visits in prior year, and date of prior CRC screening completion.

Analysis: To estimate the intervention effect, we will fit generalized linear mixed effects models (GLMM) controlling for secular trend. The basic GLMM approach to estimate intervention effects in stepped wedge studies includes an indicator for intervention and a linear or categorical input for time-period as fixed effects to control for secular trend. Given the possibility of intermittent social distancing, we will apply modifications to the basic model. First, we will examine non-linear secular trends by including splines for time-trend, which is needed if intermittent social distancing occurs and it affects outcome trends. Second, we will consider time-trend as a random effect, which allows the secular trend to vary across the CHCs. This may be needed if mandated social distancing occurs by region and differentially affects the CHCs’ secular trend. Third, we will consider interactions for time-trend and the intervention term (to allow time trend to vary pre- and post-intervention) and patient characteristics (for differential time trends by characteristics). This may be needed if subgroups (e.g. those over 60) are asked to intermittently social distance. As we cannot predict the social distancing recommendations moving forward, we describe in general terms how we will modify the basic modeling approach. Our strategy addresses the potential concerns with the basic GLMM model for stepped wedge designs in the present health climate [8]. Our modeling strategy will be informed by the judgment of the substantive experts on the investigative team with input from the CHCs and comparing models statistically using the likelihood ratio tests. The modeling approach will be used for each of the three primary outcomes. We will consider intervention effects statistically significant if we observe a p-value below 0.017 which correspond to $\alpha = 0.05$ threshold with a Šidák correction for three comparisons. If specific sub-groups of the patient population are particularly affected by social distancing, we will explore differential treatment effects by including interaction of intervention term and patient characteristic to the final GLMM model, as described.

Statistical power and sample size: We estimate that there will be 46,650 adults who need CRC screening across all of the study sites for the supplement project period and one pre-supplement period control step. Because of the nature of the CHC patient population, all patients’ situations will likely have changed and thus should receive a social needs screening. Further, we estimate that virtually all patients will have some increased social needs. To estimate power for our sample size we conducted a simulation study under three scenarios for secular trend – (1) linear small positive or flat secular trend and an intervention effect of 5% increase (3) a moderate cubic secular trend and an intervention effect of 5% increase, and (3) strong cubic

secular trend and an intervention effect of 7.5% increase. For each of these we assumed a conditional ICC of 0.10 and a baseline outcome of 50%. Each scenario incorporated the number of steps in our design, was simulated 1,000 times and modeled using the respective modifications to the basic model described above (see “Analysis”). Based on the sample size and our assumptions, we have greater than 90% power for scenarios (1) and (2), 87% power for scenario (3) at a Šidák corrected family-wise error rate of 5%. As such it is clear we have adequate power to detect a clinical meaningful effect size.

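### Does primary outcome (3), referral, need a written denominator and a rule for unscreened patients before it can be analysed?

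*Combined protocol and SAP*

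**What the plan says.** Under Outcomes, the combined protocol and SAP lists three primary outcomes: FIT return within a stated window, "completion of social needs screening", and "referral of patients with social needs to appropriate resources". Nothing further is said about the third.

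The Analysis section sets no separate analysis population for any outcome. It states: "The modeling approach will be used for each of the three primary outcomes". It also gives the threshold: "We will consider intervention effects statistically significant if we observe a p-value below 0.017".

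Study Design describes "8 months of historical controls at all of the sites", followed by a randomized roll-out, so control data come from the historical months and from sites that have not yet crossed over.

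The section on statistical power and sample size gives one total of 46,650 adults due for colorectal screening. It says that all patients are expected to need social needs screening and that almost all will have increased needs. It reports one set of power results, at a baseline of 50%, with no smaller sample for any outcome.

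**The concern.** The words of outcome (3) name a group, people with social needs, but not how its members are found. The intervention promotes screening, as the title says: "Paired Promotion of Colorectal Cancer and Social Determinants of Health Screening". Screening completion is itself outcome (2), so the plan does not take screening to be complete.

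Two readings are therefore conceivable. Over all eligible adults, outcome (3) measures screening and referral together. Over patients whose need has been identified, it measures whether known needs are acted on. On the second reading the denominator forms after the intervention starts and can be changed by it. Need status in the historical months would also have to come from records or be presumed.

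The two readings can give different answers from the same data. If the choice were made after the data were seen, one of three primary tests could depend on it.

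**Working it through.** **The plan's own figures.**

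- Threshold: 1 − (1 − 0.05)^(1/3) = 0.01695, which rounds to the stated 0.017. The two-sided critical value at 0.017 is 2.387 (sidedness is not stated; two-sided is assumed).
- Power, scenario (1): the inputs are 46,650 adults, 4 sites, baseline 50%, ICC 0.10 and a 5-point effect. A basic stepped-wedge linear mixed model with categorical periods gives standard errors of 0.80, 0.91 and 1.02 points for 5, 8 and 11 periods. Three values were tried because the number simulated is not stated. Power = Φ(5/SE − 2.387), which is above 99.9%, 99.9% and 99.4%. This agrees with the claim of more than 90%.
- The 87% for scenario (3) cannot be reproduced, because the trend parameters are not given. That is not evidence against it.

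**The two readings.** Let s be the share screened, n the share in need and r the share of screen-positive patients who are referred. Assume that referral follows screening.

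- All eligible adults, unscreened counted as not referred: rate = s × n × r.
- Identified need only: rate = r.

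Take n = 100% (the plan expects near-universal need). The values of s and r below are assumptions; the documents give none.

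| Case | All eligible | Identified need |
|---|---|---|
| s 50% to 55%, r 50% throughout | 25.0% to 27.5%, +2.5 | 50% to 50%, 0 |
| s 50% throughout, r 50% to 55% | 25.0% to 27.5%, +2.5 | 50% to 55%, +5.0 |
| s 100% throughout, r 50% to 55% | 50% to 55%, +5.0 | 50% to 55%, +5.0 |

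With need at 95% or 60%, the first all-eligible result becomes 0.95 × 0.50 × 5 = +2.4 points or 0.60 × 0.50 × 5 = +1.5 points. The identified-need result stays at 0. The readings agree in the third row because screening is complete and need is universal.

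**Which reading the plan supports.** If outcome (3) were meant for identified need only, its sample would be smaller: at 50% screened, 46,650 × 0.50 = 23,325. The power section shows no such reduction. It gives one total, one baseline and one set of results, and the Analysis section applies one approach to all three outcomes. With need expected in almost everyone, people with social needs and all eligible adults are nearly the same group. The text fits that reading better.

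**Whether a second version would add information.** With near-universal need and referral following screening, the crude rates for outcomes (2) and (3) already contain it, since r = (all-eligible rate) / s. In the first row, 25.0/50 = 50% before and 27.5/55 = 50% after. In the second, 25.0/50 = 50% and 27.5/50 = 55%. A reader with both outcomes can tell more screening from better follow-through.

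**The case for a change.** The strongest case for a change is that the power section contains planning statements, not an outcome definition. Expecting near-universal need closes the gap between all adults and all adults in need. It does not close the gap to those whose need was identified, which depends on how complete screening is. Nor does the 50% baseline settle the matter: if half of patients are screened, an all-eligible referral rate of 50% would require every screened patient to be referred (50% × 100%). A short statement would cost little and would remove a choice from a primary test.

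Much of this stands. No rule for establishing need is written, the arithmetic is right, and the two readings are different estimands. If analysts did restrict to identified need, promoted screening could alter who is included, to an unknown extent and in an unknown direction. The listed covariates, which run from demographic factors to "date of prior CRC screening completion", might reduce that but could not be relied on to remove it.

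Three things limit its force. First, the restriction that creates the selection problem is nowhere in the plan. Second, the illustration starts from an all-eligible rate of 25%, not the planned 50%, and uses referral rates that come from no document, so it cannot show the size of any effect in this trial. Third, loss of power is secondary. At 23,325 patients the same basic model gives standard errors of 1.13, 1.28 and 1.44 points, and power for 5 points of 98%, 93.5% and 86% for 5, 8 and 11 periods. The effect on scenario (3) cannot be calculated from what is given.

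**Conclusion.** The gap is real but is one of missing detail, and no change to the plan follows. The outcome names a population, and the sample-size text indicates that this is essentially all eligible adults. An analyst would fill the rest sensibly: count a recorded referral as an event, and everyone else eligible as not referred, in the same way in control and intervention periods. That denominator does not depend on who was screened, and it needs no need status for historical patients. The effect is then read as screening and referral combined, next to outcome (2).

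Under that reading no stated rule gives a wrong result, and no better method is on offer; a written definition would record the reading that the plan already suggests. The difference of 0 against +2.5 points is hypothetical. It rests on 50% to 55% screened, 50% referred, universal need, and referral only after screening.

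The conclusion rests on two assumptions: that referrals are recorded comparably in all periods, which the documents do not describe, and that the analysts keep to the all-eligible reading.

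### Replacing the single-step Šidák threshold with step-down Holm-Šidák would add power at almost no cost; separately, the adequate-power sentence should name its effect and trend

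*Combined protocol and SAP*

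**What the plan says.** **Testing rule (Analysis).** One modelling strategy serves all three co-primary outcomes: "The modeling approach will be used for each of the three primary outcomes". The decision rule is a fixed threshold: "We will consider intervention effects statistically significant if we observe a p-value below 0.017". The plan describes this as a Šidák correction of 0.05 for three comparisons. No ordering or step-down is mentioned.

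**Power (Statistical power and sample size).** Three simulated scenarios are described, each with its own trend and effect:

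| Scenario | Trend and effect | Stated power |
|---|---|---|
| (1) | "linear small positive or flat secular trend and an intervention effect of 5% increase" | above 90% |
| (2), printed as a second (3) | "a moderate cubic secular trend and an intervention effect of 5% increase" | above 90% |
| (3) | strong cubic "secular trend and an intervention effect of 7.5% increase" | 87% |

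The last column comes from the statement "we have greater than 90% power for scenarios (1) and (2), 87% power for scenario (3"). The section then concludes: "As such it is clear we have adequate power to detect a clinical meaningful effect size". The power is said to be Šidák-corrected. The section does not say whether it is power per outcome, for all three outcomes or for at least one. It gives no result for a 5% increase under the strong cubic trend and no reason for the larger effect there.

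**The concern.** **Testing rule.** With a single-step rule, each outcome faces the strictest threshold even after another outcome has already been declared significant. Family-wise control does not require that. Power is given up for the second and third outcomes, and this matters most if the intervention works on all three.

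**Power statement.** The assumed effect grows by half (5% to 7.5%) in the scenario with the strongest trend, and the conclusion that follows names neither an effect nor a trend. The plan itself allows for disturbed trends: "Given the possibility of intermittent social distancing, we will apply modifications to the basic model". If 5% is the effect of interest, the plan gives no power for it under a strong trend. If 7.5% is, the conclusion stands at 87%, but the plan should say so. Without a stated target effect, a non-significant result under a strong trend is harder to interpret.

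**Working it through.** **1. The plan's threshold.** Šidák for three tests: 1 − 0.95^(1/3) = 0.01695, which rounds to the stated 0.017. The threshold is correct.

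**2. The plan's 87%.** This cannot be reproduced, because the cubic coefficients and the exact fitted model are not given. As a check, I used a generalized least squares stepped-wedge variance with a random site intercept and the plan's inputs: 4 sites, 46,650 adults, ICC 0.10 and a 50% baseline. I assumed 5, 8, 11 or 12 periods and a linear, cubic or categorical trend. The standard error is about 0.8-1.1 percentage points, and power at 5 points is about 98-100%. The plan's strong-trend simulation therefore loses precision in a way it does not describe.

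**3. Illustrative scaling from 87%.** Assumptions: 87% is per-outcome power, the test is two-sided normal at 0.017, and the standard error is the same at both effects.
- Critical value z = 2.387; z(0.87) = 1.126; sum 3.513.
- Implied standard error: 7.5 / 3.513 = 2.135.
- Standardised effect at 5%: 3.513 × (5/7.5) = 2.342.
- Power at 5%: Φ(2.342 − 2.387) = Φ(−0.045) = 0.482.
- Monte Carlo error: √(0.87 × 0.13 / 1000) = 0.0106, so 87% has a 95% range of 84.9-89.1%, which gives 46-51% at 5%.
- Only the ratio of effects enters, so it matters little whether the 5% is absolute or relative.

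**4. Holm-Šidák thresholds.** Smallest p-value: 1 − 0.95^(1/3) = 0.01695. Second: 1 − 0.95^(1/2) = 0.0253. Largest: 0.05.

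**5. No rejection is lost.** Every step-down threshold is at least 0.01695. Any p-value at or below 0.01695 therefore passes, and so do all smaller ones. The two rules can differ to the plan's advantage only for a p-value between 0.01695 and the rounded 0.017. The first step equals the single-step test, so the chance of at least one significant outcome does not change.

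**6. Gain and error rate.** Simulation: 500,000 draws of three normal test statistics with a common correlation of 0 to 0.9 (my assumption), using the standardised effects from step 3.

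| Truth | Measure | Single-step | Holm-Šidák |
|---|---|---|---|
| All three real, 7.5% | per-outcome power | 87% | 90-93% |
| All three real, 7.5% | all three significant | 66-81% | 83-89% |
| All three real, 5% | per-outcome power | 48% | 54-56% |
| All three real, 5% | all three significant | 11-38% | 25-50% |
| Two real, 7.5% | per-outcome power | 87% | about 89-90% |
| One real, 7.5% | per-outcome power | 87% | about 87% |

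With zero, one or two real effects, the family-wise error of Holm-Šidák was 3-5%, within simulation error of the 5% limit.

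**The case against.** **The single-step rule is not an error.** It is prespecified, valid and correctly computed, and the stated power uses it. That stands. Holm-Šidák is an improvement, not the repair of a mistake. Its gain depends on more than one effect being real, and it complicates simultaneous intervals.

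**The power paragraph is open about its assumptions.** Trend and effect are given for every scenario, and the concluding sentence refers back to them. That also stands. What remains is that the plan does not identify the clinically meaningful effect, gives no strong-trend result at 5%, and does not say what kind of power it reports.

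**A reader might infer that the trial has only even odds of detecting 5% under a strong trend, or that power there must fall below 80%.** The documents do not support either. The 48% rests on one common standard error, which the plan does not give. A one-sided test would give 51.7%, and a t reference with 3 degrees of freedom 55%. If precision varied between simulated data sets, the answer could be much higher. Three invented cases, all matched to about 87% at 7.5%, show this:
- 10% of fits fail and count as non-rejections: 0.9 × 0.665 = 60% at 5%.
- Half the runs have standard error 1.0 and half 2.48: 68%.
- 80% have standard error 1.0 and 20% have 3.75: 83%.

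**The strong trend may not arise.** The plan calls social distancing a possibility and gives no likelihood for a strong cubic trend. The moderate cubic scenario is also non-linear, and there power at 5% exceeds 90%.

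**Conclusion.** The main point holds as a cheap improvement. Holm-Šidák keeps every rejection made at 0.01695 and controls family-wise error at 5% under the same conditions as the plan's Šidák rule, including valid p-values for each outcome. If 87% is per-outcome power and all three effects are real, the gain is about 3 to 6 percentage points per outcome at 7.5% and 6 to 8 at 5%. It is about zero if only one effect is real.

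The secondary point is a minor reporting gap: the adequacy conclusion is wider than the results shown. It does not show that the 87% is wrong, that 7.5% was chosen to flatter the design, or that the trial is underpowered. The 48% is an illustration under stated assumptions, neither a rerun nor a bound. Overall severity is minor and confidence moderate.

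**What to change.** **Analysis section, before outcomes are analysed.** Replace the 0.017 sentence with wording such as: The three primary p-values will be ordered from smallest to largest and compared in turn with 0.01695, 0.0253 and 0.05 (Holm-Šidák). Testing stops at the first p-value that exceeds its threshold, and that outcome and any remaining ones are declared not significant.

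**Statistical power and sample size.**
- Rerun scenario (3) at a 5% increase and report it beside the 87%, or state and justify that 7.5% is the target effect under a strong trend.
- Tie the conclusion to the results, for example: Power exceeds 90% for a 5% increase under a flat, linear or moderate cubic trend; under a strong cubic trend it is 87% for a 7.5% increase and [simulated value] for 5%.
- Say whether power is per outcome.

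**Cost.** One revised threshold sentence, one revised conclusion and at most one simulation rerun. Sites, sample size and roll-out do not change. Simultaneous confidence intervals become less simple under the step-down rule, and the reported strong-trend power may look less favourable once 5% is shown.
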